**Table 4: Participant Visit Schedule**

Phase (Length in weeks)	Screening (0)	Run-in (2 weeks)	Intervention phase 1 (4 weeks)		Wash-out (4 weeks)	Intervention phase 2 (4 weeks)		Wash-out (4 weeks)	Intervention phase 3 (4 weeks)	
Study Visit	0	No visit	Week 0 (Start)	Week 4 (End)	No visit	Week 0 (Start)	Week 4 (End)	No visit	Week 0 (Start)	Week 4 (End)
Written Informed Consent Provided	x									
Anthropometric measures										
Height	x									
Weight	x		x	x		x	x		x	x
Waist circumference	x		x	x		x	x		x	x
Blood pressure	x		x	x		x	x		x	x
Biochemical measures										
Fecal sample			x	x		x	x		x	x
24-hour urine collection (biomarkers for compliance)			x	x		x	x		x	x
Blood sample drawn			x	x		x	x		x	x
OGTT			x	x		x	x		x	x
Questionnaires										
Personal information	x									
Demographic Data	x									
Medical History	x									
Case Report Form (eg. medications, physical activity)	x		x	x		x	x		x	x
Beverage log	x	x	x	x	x	x	x	x	x	x
Symptoms questionnaire			x	x		x	x		x	x
Three-day diet record			x	x			x			x
Cravings/hunger/satiety questionnaires			x	x		x	x		x	x
Radiology										
Liver fat (MRS)			x	x		x	x		x	x

## 10.11 Outcomes

The **two primary outcomes** are change in gut microbiome beta diversity, measured by 16S rRNA gene sequencing, and plasma glucose iAUC, measured by OGTT.

**Secondary outcomes** are change in waist circumference, body weight, fasting plasma glucose, 2h plasma glucose [2h-PG], and the Matsuda whole body insulin sensitivity index [Matsuda ISIOGTT] [35].

**Exploratory outcomes** are change in blood pressure; fasting plasma insulin; 75g OGTT derived indices (iAUC plasma insulin, maximum concentrations (Cmax) and time to maximum concentrations (Tmax) of plasma glucose and insulin, mean incremental plasma glucose and insulin, homeostatic model assessment of insulin resistance (HOMA IR) and the insulin secretion-sensitivity index-2 [ISSI-2]); cardiometabolic risk (lipid panel) ectopic fat (an early metabolic lesion) in liver (intra-hepatocellular lipid [IHCL]) and calf muscles (intra-myocellular lipid [IMCL]) by H-MRS; fasting blood lipid profile; satiety, hunger, and food cravings (using the Control of Eating Questionnaire), and diet quality (by analysis of the 3DDRs)[36].

**Adherence outcomes** will be based on participant beverage logs, returned beverage containers, and objective biomarkers of SSBs (increased C/C ratios in serum fatty acids, increased urinary fructose), water (decreased C/C ratios in serum fatty acids, decreased urinary fructose), and NSBs (urinary acesulfame potassium, sucralose) intake.

### **10.12 Compliance assessment**

To assess compliance, participant beverage logs will be checked at each visit. In addition, participants will return unused SSBs, NSBs, or water bottles to assess compliance. Urinary analysis will be obtained for biomarker analysis for compliance (**Biomarkers of Adherence**, page 9).

### **10.13 Analytical Techniques**

#### **Anthropometric analyses.**

Height will be measured with a wall-mounted stadiometer (Perspective Enterprises, Portage, MI, USA).

**Body weight** will be assessed by beam scale.

**Waist circumference** will be assessed using the Heart and Stroke Foundation methodology [37].

**Blood pressure (BP) and resting heart rate** will be measured. To collect this measure, participants will remain seated in a quiet, temperature-controlled room for at least 5 minutes to achieve resting heart rate and BP.

Subsequently, BP will be measured oscillometrically using the OMRON Intellisense HEM-907 according to JNC VII criteria. BP will be measured in triplicate, with each measurement separated by one minute, and the average of the three measures will be taken [38].

#### **Biochemical analyses**

**Fecal microbiome analyses.** DNA will be extracted from fecal samples and compositional analysis will be done by next generation sequencing. Primers will be used to target the **appropriate** regions of the *16S rRNA* gene for pair-end sequencing using Illumina MiSeq [39]. Sequencing data will be analyzed to assign Operational Taxonomic Units (OTUs) to determine their abundance. Data for selected taxa will be confirmed by qPCR [40]. Alpha and beta diversity indexes will be calculated. The metagenome will be inferred from compositional data *in silico*. [41].

**Plasma Analyses.** Plasma samples for glucose and insulin will be separated by centrifuge and the plasma immediately frozen at -80 C at the University of Toronto, in a locked room, in a locked building for analysis. The BBDC at the University of Toronto will perform analyses of the plasma glucose using the glucose oxidase method [42]. The Guelph Research and Development Centre will perform the analysis for the plasma insulin using enzyme-linked immunosorbent assay (ELISA), a solid phase two-site enzyme immunoassay method using Mercodia AB Insulin ELISA (Uppsala, Sweden) kits [43] Plasma glucose and insulin curves will be plotted as the incremental change over time and iAUC will be calculated geometrically for each participant using the trapezoid method, ignoring areas below the fasting value [44]. J. Alick Little Lipid Research Laboratory at St. Michael's Hospital will perform analyses of lipids (enzymatic method). ALT will also be analyzed at St Michael's Hospital Core Lab. Remaining samples will be stored at -80 C for future analysis of metabolomics. The Matsuda ISI (Matsuda ISIOGTT) will be calculated using the 75g-OGTT derived plasma glucose (PG) and insulin (PI) values, according to the formula by Matsuda et al. [35]: 10 000 divided by the square root of ([FPGFPI] ([mean PG mean PI]), where PG is expressed in mg/dl (0.0551mmol/L) and PI in U/ml (6pmol/L). The early insulin secretion index ( $\Delta PI_{30-0}/\Delta PG_{30-0}$ ) will be calculated as the change in PI from 0 minutes to 30 minutes divided by the change in PG over the same period [45].

**Biomarkers of adherence.** Biomarkers of adherence will be assessed at the Department of Nutritional Sciences, University of Toronto by a novel gas chromatography, compound specific isotope ratio mass spectrometry (GC-CSIRMS) method that detects  $^{13}\text{C}/^{12}\text{C}$  ratios in serum fatty acids (e.g. palmitoleic acid) derived from the de novo lipogenesis (DNL) of added sugars from sugar cane (sucrose) or corn (high fructose corn syrup [HFCS]) will assess adherence to SSBs (increased) or water (decreased). A liquid chromatography with mass spectrometry using electrospray ionization (LC-ESI-MS/MS) will be used to assess urinary sucralose or acesulfame potassium (Ace K) [46]. Urinary fructose will be measured by gas chromatography mass spectrometry (GS-MS) [47].

#### Questionnaires

**Dietary Assessment.** Participants will be asked to fill out a weighed 3DDR using Nutritics, a nutrition software available for use on smartphones. The 3DDR will consist of two non-consecutive weekdays and one weekend day during the run-in phase and during the last week of each intervention. If participants do not have access to a smartphone, a paper form of the 3DDR will be provided. Participants will also be provided with scales to insure the accuracy of the record. Registered dietitians will instruct and review 3DRDs with participants. The 3DRDs will be used to evaluate changes in diet quality and will be analyzed by using Nutritics. Food cravings, hunger, and satiety will be assessed using modified Corby Martin's Questionnaires [48].

**Behavior of beverage consumption** will be assessed with a product consumption questionnaire. This will be done at the last visit for the participants that are still enrolled in the study and via telephone or email for the participants that have completed the study.

#### Radiology

**Liver and calf muscle fat.** We will use a 3T Siemens Magnetom Skyra scanner (Erlangen, Germany) with either an 18 channel body phased array coil or a dedicated peripheral phased array coil. Single voxel, 30mm cubed spectroscopy will be acquired for IHCL and IMCL using a STEAM (Stimulated Echo Acquisition Mode) sequence and the following acquisition parameters: TR 3000 ms, multiple TE values 12 ms, 24 ms, 36 ms, 48 ms, 72 ms, mixing time (TM) 10 ms, 10 averages, 1024 data points and receiver bandwidth 1200 Hz for an acquisition time under one minute. Participants will be scanned for 30 minutes.

Our **Postdoctoral Fellow ([name], MBBS, PhD)** will coordinate all analyses and our **MSc candidate #2 ([name] )** will conduct fecal microbiome analyses.

**10.14 Study duration.** Each participant will be enrolled for approximately 6 months (~164 days) and will undergo 1 x 2-week run-in phase, 3 x 4 week interventions and 2 x 4 week wash-out phases. All participants will undergo each intervention for four weeks, the order being randomly assigned. The entire study is expected to take approximately 4 years to complete, allowing for ethics and material/data transfer agreement approvals (6 months), rolling recruitment (6-months), run-in phase, intervention (x3) and washout (x2) phases (total 6-months), microbiome/ plasma/ imaging/ biomarker analyses (9-months), data analyses (9-months), and final write-up (6-months).

**10.15 Data Integrity/Management.** All paper copies of data forms will be stored under a double lock system to ensure confidentiality (locked cabinet in a locked office). Only PI, co-investigators and assigned study personnel will have access to the cabinet. The participant digital database will be securely stored centrally at SMH. The data management system enables anonymized and secure information storage, retrieval and sharing and will be organized and supported by the Li Ka Shing Knowledge Institute IT team of St. Michael's Hospital. All data forms will be stored under a double lock system to ensure confidentiality. Only the PI, co-investigators and assigned trial personnel will have access to the cabinet. The Applied Health Research Centre (AHRC), St. Michael's Hospital, will be contracted to manage the digital database securely and ensure data integrity. Their data management system enables anonymization, secure information storage, retrieval, and sharing of data.

**10.15 Personal Health Information.** We will be collecting personal health information during this study. The personal health information will include name, phone number, email address, demographic information, health

history, questionnaires and records, and research visit records. In order to keep participant data confidential, we will create a master linking log which will separate identifying data (name and contact information) from study data with a study ID. The master linking log will be kept in a password-protected file on a drive through St Michael's Hospital computer, only accessible to study staff and investigators. Any subject requesting access to their personal health information will be able to do so by requesting this through the study coordinator.

**10.16 Subject Compensation.** Once participant is randomized travel compensation will be provided. To compensate for lengthy time required for study visits, each participant will be compensated \$80 for first 5 visits and \$95 for final visit, totaling \$495 for completing the trial. Participants will receive payment at the end of each phase (three times during the study). However, they will be informed that if they choose to withdraw early, they will be compensated for each visit that was completed. Transportation costs (i.e. parking or TTC tokens) will be reimbursed and breakfast will also be provided at each study visit. Any transportation costs incurred for additional visits for obtaining stool and urine collection kits will be reimbursed as well.

#### **10.17 Anticipated Challenges**

**Recruitment challenges.** We require individuals who are regular SSB drinkers. In fact, soft drinks are the second largest source of added sugars for adults in Canada [49] and the per capita intake of SSBs in Canada is 0.9 with estimated 20 percent drinking more than 1 SSB serving per day [50]. Even if half of this population drinks NSBs, there is estimated 10 percent adult population that drinks more than 1 SSB serving per day. In addition, we plan to recruit from overweight and obese individuals who are known to have a higher SSB intake [51].

**Compliance challenges.** In dietary studies, compliance is usually a challenge. We will address this by having participants keep beverage logs at all phases of the trial including run-in and washout phases. Participants will be able to select a brand of beverage they like in both NSB and SSB arms. These beverages will be provided to the participants from the study site for the first week of each phase and shipped via Starhawk express for the three subsequent weeks. In addition, adherence to treatment will be reinforced with regular phone calls and/or emails to the participants. Since the intervention consists of a wide range of easily available supermarket drinks (**Table 3**), we do not anticipated challenges in acceptance on basis of palatability, taste or volume.

**Protocol compliance.** Those who use antibiotics during an intervention phase will have to go through a 30 day washout period at the completion of their antibiotic course and restart that phase of intervention. If the antibiotic course is taken during the washout phase, a 30 day additional washout will be instituted.

### **11. Statistical Analysis**

Data will be analyzed according to an intention to treat (ITT) principle using mixed models in STATA 14 (StataCorp, Texas, USA). Sensitivity analysis will be performed on the basis of complete data availability for primary endpoints. A separate sensitivity analysis will be performed on the basis of antibiotic use during the trial.

**Primary outcomes.** Repeated measures mixed effect models will be used to assess changes in the two primary outcomes i) beta diversity and ii) glucose iAUC between the groups. Pairwise comparisons between interventions will be performed using Tukey-Kramer adjustment or other appropriate statistics. For all primary outcomes effect modification by sex will be explored. We will use the truncated Benjamini-Hochberg false discovery rate controlling method with parallel gatekeeping procedure to correct for multiple comparisons for all primary outcomes [32].

**Secondary outcomes.** Repeated measures mixed effect models be used to assess changes in weight, waist circumference, fasting glucose, 2hr plasma glucose, and MATSUDA. Pairwise comparisons between interventions will be performed using Tukey-Kramer adjustment or other appropriate statistics. For all secondary outcomes

effect modification by sex will be explored. We will use the truncated Benjamini-Hochberg false discovery rate controlling method with parallel gatekeeping procedure to correct for multiple comparisons for all secondary outcome comparisons [33] if at least one primary outcome reaches significance. If none of the primary outcomes reach significance, the secondary outcomes will be analyzed as exploratory variables with no adjustment for false discovery rate.

**Exploratory and adherence outcomes.** Repeated measures mixed effect models will be used to assess changes in all exploratory outcomes without controlling for false discovery rate. Pairwise comparisons between interventions will be performed using Tukey-Kramer adjustment or other appropriate statistics. Effect modification by sex will be explored.

**Subgroup Analysis.** A priori analysis will be conducted by age, sex, ethnicity, baseline BMI, baseline WC, baseline FPG, baseline 2hPG (OGTT), baseline iAUC, medication use, sweetener blend (intervention), beverage type (intervention), and background sweetener use.

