## 9. HYPOTHESIS

[figure not shown]
1. Replacing SSBs with NSBs or water will change the diversity of gut microbiome after four weeks in regular SSB drinkers.
2. Replacing SSBs with NSBs or water will increase glucose tolerance after four weeks in regular SSB drinkers.
3. Replacing SSBs with NSBs or water will decrease body weight, reduce blood pressure, improve glucose and insulin regulation, decrease blood lipids, decrease ectopic fat, decrease liver fat, decrease body adiposity, and improve diet quality after four weeks in regular SSB drinkers.

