**Figure 1: Overview of the study visits and phase.\***

\*All possible groups are not shown.

**10.02 Blinding.** Blinding of the participants and investigators will not be possible due to packaging, taste and look of the interventions. However, outcome assessors (laboratory, microbiome analysis) and the statistician will be blinded to the identity of the treatments.

**10.03 Participants.** We will recruit 81 overweight or obese (ethnic specific cut-offs for overweight and obesity are used  $\geq 23$  kg/m^2 for Asian individuals and  $\geq 25$  kg/m^2 other individuals[11]), adult (age, 18-75 years) men and non-pregnant women (with no conception plans for the study duration) with a high waist circumference ( $\geq 94$ cm in men,  $\geq 80$ cm in women in Europid, Sub-Saharan African, Eastern Mediterranean, and Middle Eastern individuals;  $\geq 90$ cm in men and  $\geq 80$  cm in women for South Asian, Chinese, Japanese, and South and Central American individuals[26]) who are otherwise healthy (free of disease or illness), not taking medications that have a clinically relevant effect on the primary outcomes, not smoking, have no intentions of making major alterations to their diet or physical activity regime during study duration, and consuming  $\geq 1$  servings of SSBs per day (for which there is an NSB equivalent that contains the non-nutritive sweeteners acesulfame potassium or sucralose). Participants must be agreeable to consume only one type of SSB and brand-matched NSB for each month of intervention. If participants are consuming NSBs in addition to SSBs they must be willing to forgo them for the run-in and duration of the study. All participants must have a primary care physician and be proficient in English to be eligible for the study. Please see **Table 1** for a full set of exclusion criteria. SSBs will be defined as any sugar-sweetened beverage (sodas and soft drinks) that contains at least 50 kcal per 8-oz serving. For the purpose of the study, SSBs will NOT include fruit drinks, sports/energy drinks, sweetened iced tea, coffee, or homemade SSBs such as frescas or 100% fruit juice. All participants will be expected to participate in the study for approximately six months (one run-in phase of two weeks, three intervention phases of four weeks each, and two wash-out phases of four weeks each) and be able to attend all study visits. They must consent to have the

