#### **10.04 Sample Size (Power) Calculation.**

The study will be performed in a total of 81 participants. It is powered to show a difference between the water, NSB, and SSB arms in 60 participants in the two primary outcomes. Assuming a drop-out rate of 20 percent, we

would need 75 participants in order to have the power to detect a difference. Since our final recruitment strategy resulted in a large number of participants who made it through the run-in phase, we decided to increase our recruitment in order to replace drop outs and thus will recruit 81 participants.

One primary outcome is in beta diversity of the gut microbiome communities of the participants between water and NSB groups via 16S ribosomal rRNA gene sequencing. We used the micropower R package to compute sample size based upon the power of 16S tag sequencing that can be analyzed using pairwise weighted UniFrac distances [28]. UniFrac is a distance metric based upon the unique fraction of branch length in a phylogenetic tree built from two sets of taxa. Comparison of microbiome samples is performed via weighted UniFrac, which considers the relative abundance of taxa. We simulated the within-group distance as 0.2, and the standard deviation (SD) of within-group distances as 0.07. To detect a weighted UniFrac distance of 0.04, which is smaller than the effect observed in a study of Suez et al. [29] (0.05 derived from figure 5), and considering it is a cross-over study with a within-person correlation of 0.7, and taking into account multiple arms we calculated that for above 95 percent power we would need 60 participants in this study. Assuming a loss of 20 percent, we will recruit 75 participants. We are confident about detecting an alteration in gut microbiome diversity if it exists as previous studies show that small changes in diet causes significant alteration in gut microbiome taxa over a much shorter period (5 to 7 days) in fewer individuals (10 to 25 people) [25, 30].

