**Table 2. Power calculation for primary outcomes between water and NSB arms**

Outcome type	Outcome	Mean change	SD	Correlation	N	Alpha*	Power (Beta)	N (corrected for 20% loss to follow up)
Primary outcomes family								

Primary	Microbiome UniFrac Distance	0.04	0.07	0.7	60	0.0375	98%	75
Primary	Glucose iAUC	44.81 mmol/L/min (20%)	113 mmol/L/min	0.7	60	0.025	89%	75

P-value order will be from largest to smallest.

**10.05 Recruitment.** Participants will be recruited through postings and flyer handouts at St. Michael's Hospital, the University of Toronto, local clinics, and surrounding areas, advertisements in newspapers and on transit, and online listings on Craigslist and Kijiji. Some participants will complete a Survey Monkey to assess general eligibility. We will be utilizing a digital marketing group, TrialFacts, to launch a campaign to recruit participants. TrialFacts works exclusively with research groups to provide specialized patient recruitment services for clinical trials. Participants will be screened first by telephone. Eligible participants will be called in for an information session on the study including being provided the consent form. Those that wish to participate will provide written consent and will subsequently have an in-person screening including blood work. Based on our most recent FACE trial (NCT02459834), we estimate a recruitment rate of 1-2 participants/week and therefore plan to recruit all the participants within a 6-month period. **[name]** will organize the recruitment. Our **MSc candidate #1 ([name], RD)** and our **Research Coordinator** will conduct the screening.

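### The microbiome primary outcome is sized on pairwise weighted UniFrac distances, but Section 11 puts beta diversity in a mixed model without defining the value per participant and visit, so the 98% power is not shown for the planned test

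*Combined protocol and SAP*

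**What the plan says.** - **Outcome.** Section 10.11 gives the first primary outcome as a change in beta diversity from 16S sequencing. It names no metric, reference sample or per-visit value. Section 10.13 says that diversity indexes will be computed, without a formula. For glucose, the same section defines iAUC fully (trapezoid rule, area below fasting ignored).
- **Sizing.** Section 10.04 uses the micropower package for the power of 16S data "that can be analyzed using pairwise weighted UniFrac distances", and adds: "Comparison of microbiome samples is performed via weighted UniFrac". The inputs are stated thus: "We simulated the within-group distance as 0.2, and the standard deviation (SD) of within-group distances as 0.07". The effect is 0.04 for water vs NSB, with within-person correlation 0.7. The cited source of the method (reference 28) has pairwise distances and PERMANOVA in its title, the only place where PERMANOVA is named.
- **Power table (Table 2 in Section 10.04).** The row "Microbiome UniFrac Distance" has mean change 0.04, SD 0.07, correlation 0.7, N=60, alpha 0.0375 and power 98%.
- **Analysis.** Section 11: "Repeated measures mixed effect models will be used to assess changes in the two primary outcomes i) beta diversity and ii) glucose iAUC". Pairwise comparisons use Tukey-Kramer or an unnamed alternative. Section 11 names neither weighted UniFrac nor PERMANOVA.
- **Expected effect.** Section 9: "Replacing SSBs with NSBs or water will change the diversity of gut microbiome after four weeks".
- **Blinding.** Section 10.02: "outcome assessors (laboratory, microbiome analysis) and the statistician will be blinded to the identity of the treatments".

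**The concern.** Glucose iAUC is one number per participant and visit. A UniFrac distance belongs to a pair of samples, so it must be reduced before a mixed model can use it. The candidates include distance from the participant's own Week-0 sample (self-distance), distance to a group centroid, or a score on an ordination axis. An independent analyst could not run this primary analysis as written.

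The candidates also answer different questions. Self-distance asks whether the arms moved equally far. It cannot see two communities that moved equally far in different directions, and it reacts to a change in spread. That matters here. Section 9 expects diversity to change with NSBs or water, and Section 10.09 returns participants to their usual SSBs during wash-out, so both arms may move from an SSB baseline. A null result on self-distance could then be misread as evidence that NSBs resemble water, which is the question Section 12 says the trial will clarify.

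The result also counts beyond this outcome. Under Section 11, one significant primary outcome is enough for the secondary family to be tested with false discovery rate control.

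**Working it through.** **1. The plan's own figure.** The micropower simulation cannot be rerun, because its community settings are not given. As a check, treat the table's inputs as a scalar in a paired t-test: n=60, difference 0.04, two-sided alpha 0.0375 (sidedness is not stated). Noncentrality = 0.04 / (SD of difference / √60).

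| Reading of SD 0.07 and r 0.7 | SD of difference | Noncentrality | Power |
|---|---|---|---|
| Week-4 contrast | 0.07 × √(2 × 0.3) = 0.0542 | 5.71 | 99.98% |
| 0.07 is already the SD of the difference | 0.07 | 4.43 | 98.8% |
| Contrast of changes, r 0.7 between all visits | 0.07 × √(4 × 0.3) = 0.0767 | 4.04 | 97.0% |

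All three are within 2 points of 98%, so the figure is arithmetically plausible. They lie too close to the ceiling to identify the method. The correlation matters: the Week-4 contrast gives 83.9% at r=0, 94.4% at 0.3 and 98.8% at 0.5. Neither 0.07 nor 0.7 is tied in the text to a per-participant value.

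**2. Does the choice of value matter?** Illustration only; the following are assumptions. Gaussian coordinates in 3, 4 or 8 dimensions stand in for UniFrac, scaled to mean within-group distance 0.20. Correlation is 0.7 between all visits, n=60, alpha 0.0375, with 1,000 trials and 399 permutations per setting. The implied SD of distances is 0.084, 0.073 and 0.051, so only 4 dimensions is close to the plan's 0.07. Ranges cover the three dimensions and repeat runs.

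| True effect at Week 4 | Self-distance, paired t | Within-participant permutation test, Week-4 distances |
|---|---|---|
| Only NSB moves, 0.04 | 8–22% | 95–100% |
| Only NSB moves, 0.10 | 93–100% | 100% |
| Only NSB moves, 0.14 | 100% | 100% |
| NSB and water each move 0.10, perpendicular | 3–5% | 100% |

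The last two rows have the same separation between arms: √(0.10² + 0.10²) = 0.141. In both, the mean between-arm distance is about 0.04 above 0.20. Self-distance power falls from 100% to about alpha because the two arms move equally far.

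With no shift, but NSB Week-4 within-person spread multiplied by 1.5, self-distance rejects in 86–100% of trials at 0.05. The permutation test rejects in 3.6–6.0%.

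**3. Should Week-0 be subtracted?** Let b be the correlation between periods and w the correlation within a period. Per coordinate, the variance of the Week-4 contrast is 2σ²(1 − b), and of the contrast of changes 4σ²(1 − w). Change is more precise when w > (1 + b)/2, which is 0.85 at b=0.7.

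- All correlations 0.7, shift 0.04: change has 71.0 / 83.8 / 98.4% (3 / 4 / 8 dimensions), against 96.0 / 98.9 / 100% for Week-4 alone.
- w=0.9, b=0.7: change 100%, Week-4 alone 98.8%.
- w=0.8, b=0.5: change 94%, Week-4 alone 90%.

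The plan gives a single correlation and does not say which visits it links, so it does not settle this choice.

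**The case against.** The strongest reply is that much is already fixed. Section 10.04 names the metric and the contrast. The power table gives a mean change, SD and correlation, as one would for a scalar. The statistician is blinded. All of this stands and narrows the gap. It does not close it: the table does not say which distance changes, and the SD is described as that of within-group distances. Blinding lowers the risk of a data-driven choice, but coded labels still show which value separates the arms.

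The second reply is that the low powers come from an assumed geometry. That also stands. No passage gives the direction or size of movement in either arm, and perpendicular movement is a worst case. In a similar simulation, self-distance power for a 0.04 shift was 15%, 29% and 70% at 5, 10 and 30 dimensions.

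Three stronger readings are tempting and are not supported:

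- **That the 98% is wrong or the trial underpowered.** Simple scalar readings return 97.0–99.98%.
- **That the microbiome and glucose rows must come from one formula.** Section 10.04 says the microbiome row used micropower, so they need not.
- **That Week-0 should not be subtracted.** This holds only under equal correlation across visits, and Section 10.11 defines the outcome as a change.

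**Conclusion.** The concern holds as a missing link. The response of one of the two primary analyses is undefined, and the power offered for it belongs to a distance-based method that Section 11 does not plan. This conclusion rests on the text alone and is firm.

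The size of the consequence is conditional. In the simulated settings, self-distance ranges from about alpha to 100% power, while a test matched to the sizing stays at about 95% or more. Those figures assume a Euclidean stand-in for UniFrac, 3 to 8 dimensions and a correlation of 0.7 between all visits. They show that the choice matters; they do not predict this trial's power. A reader might take the 3–5% as the expected power of the planned analysis. The documents do not support that, because they neither select self-distance nor describe perpendicular movement.

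**What to change.** Before unblinding, amend Sections 10.11 and 11 in one of two ways.

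**Preferred: match the test to the sizing.**
- Make the primary NSB vs water test a weighted UniFrac PERMANOVA, with permutations restricted within participant and period fitted first.
- Prespecify how Week-0 enters: a fixed number of Week-0 principal coordinates as covariates, or a change. Justify the choice by the expected within-period and between-period correlations.
- Prespecify one adjustment for the three contrasts. Enter the adjusted p-value, with the adjusted glucose p-value, in the truncated Benjamini-Hochberg step. The table's note reads "P-value order will be from largest to smallest", so the larger p-value is judged at 0.0375 and otherwise the smaller at 0.025.
- Add a dispersion check. Keep mixed models on prespecified scalars, using all available periods, as supportive.

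**Alternative: keep the mixed model primary.** Define its scalar exactly (metric, reference sample or axis, visits), and restate the table's power from an SD and correlation for that scalar.

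**Cost.** No new data. The preferred route needs a permutation routine outside the mixed model. Participants with only one of the two periods drop out of that contrast, so the number contributing should be reported. If 20% are lost, half after period 1 and half after period 2, the fraction with both periods is 0.8 + 0.2 × 1/2 × 1/3 = 0.833. That is about 67 of 81 or 62 of 75, still above the 60 used for sizing. The alternative costs only text and a restated power line.
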